7.2 Number of Subjects

Approximately 40 subjects with wet AMD will be enrolled at approximately 10 sites. The final number of subjects enrolled may be adjusted based on drop-out rate. Subjects that successfully exited TOFU study on or before approximately September 1, 2021 will be considered for RAMEN Study

7.3 Treatment Assignment

RBM-007 injectable solution 2.0 mg (100 µL of 20 mg/mL) will be administered by IVT injection in the study eye.

7.4 Dose Adjustment Criteria

The Safety Review Team will review safety parameters periodically and in the event of any SAE for adjusting or stopping doses.

7.5 Study Procedures

All subjects must sign a written ICF before participating in any study-related activity. Once the subject meets all eligibility requirements at Screening Procedure - Visit 1 (Baseline (Day1)), each subject will continue to be assigned with the unique subject number provided in TOFU study. If a subject is discontinued from the study for any reason, the subject number will remain in effect and will not be reused.

A Schedule of Events can be found below and detailed procedures for examinations can be found in [Section 21.4](#), Appendix D – Procedures for Examinations.

Table 2: Schedule of Events

Visit Number	Visit 1 (SCRN/Injection)		Visit 2 (Injection)		Visit 3 (Injection)		Visit 4 (Injection)		Visit 5	Visit 6 (Exit)
Visit Schedule (Time window; days)	D1		M1		M2		M3		M4	M5
			D29 (±4)		D57 (±4)		D85 (±4)		D113 (±7)	D141 (±7)
	Pre	Post	Pre	Post	Pre	Post	Pre	Post		
Informed consent ^a	X									
Demographics/Eligibility	X									
Medical/surgical history, Concomitant medication	X		X		X		X		X	X
Physical examination	X									X
Vital signs	X									X
BCVA (ETDRS)	X		X		X		X		X	X
External ocular exam	X		X		X		X		X	X
Intraocular pressure (IOP) ^b	X	X	X	X	X	X	X	X	X	X
Slit-lamp biomicroscopy ^c	X	X	X	X	X	X	X	X	X	X
Indirect ophthalmoscopy ^c	X	X	X	X	X	X	X	X	X	X
SD-OCT	X		X		X		X		X	X
OCT Angiography ^d	X									X
Fundus photography	X		X		X		X		X	X
Fundus autofluorescence	X									X
Urine pregnancy test ^e	X									X
IVT injection	X		X		X		X			
Adverse event	X		X		X		X		X	X

SCRN = Screening; D = Day; M = Month;

^a Informed Consent to be obtained prior to conducting any study-related activities.

^b IOP will be performed before the IVT injection and 30 (±10) minutes after the IVT injection. If IOP is > 21 mmHg after eye massage and/or aqueous tap performed per investigator discretion, perform IOP again at 60 (±10) minutes after the injection. If IOP is still > 21 mmHg after eye massage and/or aqueous tap performed per PI discretion, perform IOP again at 90 (±10) minutes after the injection. This will be also applied for the post IVT injection of Rescue treatment.

^c On days when any IVT injections are administered, slit lamp biomicroscopy and indirect ophthalmoscopy will be performed prior to the injection and within 30 minutes after the injections. This will be also applied for the post IVT injection of Rescue treatment.

^d Selected sites will conduct OCT angiography in all subjects.

^e Urine pregnancy tests are to be performed on all women of child-bearing potential.

7.5.1 Study Visits

7.5.1.1 Visit 1 (Baseline (Day 1))

[figure not shown]
Screening Procedure:

- Ascertain the patient has successfully exited TOFU study.
- Visit 1 should happen during 0 to 60 days after the exit Visit in TOFU Study.
- Ascertain the patient has exudative AMD.
- Ascertain the patient did not have improvement of vision more than 15 letters of BCVA at the exit visit of TOFU study over its baseline.
- Explain the purpose and details of the study to the subject and obtain written informed consent prior to the subject's participation in any study related activity.
- Review subject's demographic information, medical, surgical and medication history.
- If the subject continues to be eligible for the study, ask female subject whether she is postmenopausal ([Section 21.4.4](#)). Perform urine pregnancy test to the subject who answered "No" to the question.
- Perform the following assessments (all ophthalmic procedures to be performed on both eyes):
 - Physical examination
 - Vital signs
 - BCVA (ETDRS)
 - External ocular exam
 - IOP
 - Slit-lamp biomicroscopy
 - Indirect ophthalmoscopy
 - SD-OCT
 - OCT Angiography
 - Fundus photography
 - Fundus Autofluorescence
- Review the inclusion and exclusion criteria. Do not continue screening any subject who does not meet the screening eligibility requirements.

Treatment Procedure

- After review, if the subject continues meeting all eligibility criteria, confirm the study eye is same as in TOFU study, and proceed for the injection that will be administered as per drug labeling.
- Administer IVT RBM-007 as per drug labeling.
- The following assessments must be performed after the injection (only on the treated Study Eye):
 - Within 30 minutes post-injection:
 - ✓ Slit-lamp biomicroscopy
 - ✓ Indirect ophthalmoscopy
 - IOP will be measured at 30 (± 10) minutes post-injection.
 - If post-injection IOP is > 21 mmHg after eye massage and/or aqueous tap performed per investigator discretion, IOP measurement will be repeated at 60 (± 10) minutes post-injection.
 - If post-injection IOP at 60 (± 10) minutes is > 21 mmHg after eye massage and/or aqueous tap performed per investigator discretion, IOP measurement will be repeated at 90 (± 10) minutes post-injection.
 - If there is an increase of ≥ 10 mmHg at 90 (± 10) minutes post-injection compared to pre-injection IOP, the subject should be prescribed a topical IOP-lowering medication until he or she returns for follow-up per the Clinical Investigator's discretion (an unscheduled visit may apply).
 - On the other hand, a subject with IOP measurement of > 21 mmHg will be managed according to the discretion of the Clinical Investigator.
 - The IOP increase of ≥ 10 mmHg from pre-injection AND IOP measurement of > 21 mmHg will be reported as an AE.
- Aqueous tap can be performed at any time per the Clinical Investigator's discretion for treatment or prevention of an increase in the IOP (see [Figure 1](#)).
- AE assessments must be performed after IVT injection.
- Upload collected images (SD-OCT and Fundus photography) of the study eye to the Egnyte server.
- Schedule the subject to return for Visit 2 (Month 1 (D29 ± 4)).

Figure 1: Decision IOP Process for IVT Injection

7.5.1.2 Visit 2 (Month 1 (D29±4))

- Perform the following assessments (all ophthalmic procedures to be performed on both eyes):
 - Query for AEs

- Update medical history and medications
- BCVA (ETDRS)
- External ocular exam
- IOP
- Slit-lamp biomicroscopy
- Indirect ophthalmoscopy
- SD-OCT
- Fundus photography

- **Injection/ IOP control procedures are same as Visit 1 (Baseline (Day1)), described in Section 7.5.1.1**
- Upload collected images (SD-OCT and Fundus photography) of the study eye to the Egnyte server.
- Schedule the subject to return for Visit 3 (Month 2(D57±4)).

7.5.1.3 Visit 3 (Month 2 (D57±4))

- Perform the following assessments (all ophthalmic procedures to be performed on both eyes):
 - Query for AEs
 - Update medical history and medications
 - BCVA (ETDRS)
 - External ocular exam
 - IOP
 - Slit-lamp biomicroscopy
 - Indirect ophthalmoscopy
 - SD-OCT
 - Fundus photography
- **Injection/ IOP control procedures are same as Visit 1 (Baseline (Day1)), described in Section 7.5.1.1**
- Upload collected images (SD-OCT and Fundus photography) of the study eye to the Egnyte server.
- Schedule the subject to return for Visit 4 (Month 3 (D85±4)).

7.5.1.4 Visit 4 (Month 3(D85±4))

- Perform the following assessments (all ophthalmic procedures to be performed on both eyes):
 - Query for AEs
 - Update medical history and medications
 - BCVA (ETDRS)
 - External ocular exam
 - IOP
 - Slit-lamp biomicroscopy
 - Indirect ophthalmoscopy
 - SD-OCT
 - Fundus photography
- **Injection/ IOP control procedures are same as Visit 1 (Baseline (Day1)), described in Section 7.5.1.1**
- Upload collected images (SD-OCT and Fundus photography) of the study eye to the Egnyte server.
- Schedule the subject to return for Visit 5 (Month 4 (D113±7)).

7.5.1.5 Visit 5 (Month 4 (D113±7)): Primary Endpoint

- Perform the following assessments (all ophthalmic procedures to be performed on both eyes):
 - Query for AEs
 - Update medical history and medications
 - BCVA (ETDRS)
 - External ocular exam
 - IOP
 - Slit-lamp biomicroscopy
 - Indirect ophthalmoscopy
 - SD-OCT
 - OCT Angiography
 - Fundus photography
 - Fundus autofluorescence
- Upload collected images (SD- OCT, Fundus photography and Fundus autofluorescence) of the study eye to the Egnyte server.
- Schedule the subject to return for Visit 6 (Month 5 (D141±7)).

7.5.1.6 Visit 6/Exit (Month 5 (D141±7))

- Perform the following assessments:
 - Query for AEs
 - Physical Exam
 - Vital Signs
 - Update medical history and medications
 - Perform urine pregnancy test to the subject who answered “No” to the question on postmenopausal at *Visit 1 (Baseline (Day 1))*.
 - BCVA (ETDRS)
 - External ocular exam
 - IOP
 - Slit-lamp biomicroscopy
 - Indirect ophthalmoscopy
 - SD-OCT
 - Fundus photography
- Upload collected images (SD-OCT and Fundus photography) of the study eye to the Egnyte server.

7.5.2 Unscheduled Visits

If a subject requires evaluation between scheduled visits, complete all applicable study specified procedures as necessary and record the information on the Unscheduled Visit form(s).

8 SELECTION AND WITHDRAWAL OF SUBJECTS

Eligible subjects must meet all eligibility criteria described in [Section 8.1](#) and [Section 8.2](#).

8.1 *Subject Inclusion Criteria*

At *Visit 1 (Baseline (Day 1))*, subjects must meet all of the following inclusion criteria:

1. Provide signed written informed consent on the Institutional Review Board (IRB)/Ethics Committee (EC) approved Informed Consent Form (ICF) and provide authorization as appropriate for local privacy regulations.
2. Male or female 55 years of age or older on the date of signing the ICF and able and willing to comply with all treatment and study procedures.
3. Subjects must have completed all scheduled visits of TOFU study. Subjects can only enter this study after exiting TOFU study
4. Subjects for which previous TOFU masked treatment arms with intravitreal anti-vascular endothelial growth factor (anti-VEGF) agents Eylea® and/or RBM-007 has not demonstrated improvement in vision; subjects with less than 15 letter BCVA improvement in TOFU study at exit visit over its baseline.
5. Diagnosis of exudative AMD in the study eye, as assessed by spectral domain optical coherence tomography (SD-OCT).
6. Absence of central atrophy or retinal epithelial tear in the fovea or any condition preventing VA improvement in the study eye.
7. BCVA of 24 ETDRS letters (20/320) or better in the fellow eye
8. Reasonably clear media and some fixation in the study eye to allow for good quality SD-OCT and fundus photography.

8.2 *Subject Exclusion Criteria*

A subject with any of the following conditions is not eligible to participate in the study:

Ocular:

1. Subjects whose vision have improved >15 BCVA letters at exit visit of TOFU study over its baseline
2. Subjects who experienced any drug related serious adverse event during TOFU study
3. Use of any of the following treatments or anticipated use of any of the following treatments to the study eye:

- a. Intravitreal or periocular corticosteroid, within 90 days prior to Visit 1 (Day 1) and throughout the study.
- b. Fluocinolone acetonide intravitreal implant, within 12 months prior to Visit 1 (Day 1) and throughout the study.
- c. Visudyne® photodynamic therapy, within 90 days prior to Visit 1 (Day 1) and throughout the study.
4. Uncontrolled or advanced glaucoma, evidenced by an IOP of > 21 mmHg or cup/disc ratio > 0.8 while on medical therapy, or chronic hypotony (< 6 mmHg) in the study eye.
5. Evidence of any other ocular disease other than wet AMD in the study eye that may confound the outcome of the study (e.g., active diabetic retinopathy, posterior uveitis, pseudo vitelliform macular degeneration, moderate/severe myopia).
6. History of vitrectomy in the study eye.
7. Need for ocular surgery in the study eye during the course of the study.
8. YAG laser capsulotomy within 30 days prior to Visit 1 (Day 1) in the study eye.
9. Intraocular surgery, including lens removal or laser, within 90 days prior to Visit 1 (Baseline (Day 1)) in the study eye.
10. Ocular or periocular infection in either eye.
11. Pupillary dilation inadequate for quality fundus photography in the study eye.
12. Media opacity that would limit clinical visualization, fundus photography, fundus autofluorescence, or SD-OCT evaluation in the study eye.
13. History of herpetic infection in the study eye or adnexa.
14. Presence of known active toxoplasmosis, inactive toxoplasmosis or toxoplasmosis scar in either eye.
15. Presence of any form of ocular malignancy including choroidal melanoma in either eye.

Non-Ocular:

16. Prior systemic treatment with RBM-007 injectable solution.
17. Use of any of the following treatments or anticipated use of any of the following treatments during the study:
 - a. Systemic treatment with anti-VEGF agents (e.g., bevacizumab)
 - b. Agents targeting the FGF-2 pathway
18. Allergy or hypersensitivity to study drug product, fluorescein dye, or other study related procedures/medications.
19. Major surgery within 90 days prior to Visit 1 (Baseline (Day 1)). Major surgery is defined as any surgery involving a risk to the life of the subject, including any operation upon an organ within the cranium, chest, abdomen, or pelvic cavity.

20. Therapeutic radiation to the head or neck within 90 days prior to Visit 1 (Day 1).
21. Participation in other investigational drug or device clinical trials within 30 days prior to Visit 1 (Baseline (Day 1)) or planning to participate in other investigational drug or device clinical trials for the duration of the study. This includes both ocular and non-ocular clinical trials.
22. History of other disease, metabolic dysfunction, physical examination finding, or clinical laboratory finding giving reasonable suspicion of a disease condition that contraindicates the use of an investigational drug, might affect the interpretation of the results of the study, or renders the subject at high risk for treatment complications.
23. Females who are pregnant or lactating and females of child-bearing potential who are not using adequate contraceptive precautions (i.e., IUD, oral contraceptives, barrier method, or other contraception deemed adequate by the Clinical Investigator).
24. Unable to comply with study procedures or follow-up visits.

In addition, the Clinical Investigator or RIBOMIC Medical Monitor may declare a subject ineligible for any sound reason.

8.3 Subject Withdrawal Criteria

An early termination occurs when a subject who provides written informed consent ceases participation in the study, regardless of circumstances, before the completion of the study. Subjects may voluntarily withdraw from the study at any time for any reason. In addition, the Clinical Investigator or the Medical Monitor may terminate a subject's study participation for reasons related to the best interest of the subject. Subjects who terminate from the study may be replaced. Subjects may be terminated from the study due to any of the following reasons:

- Non-compliance
- Lost to follow-up
- Protocol violation
- Withdrawal by subject
- AEs
- Death
- Other

If a subject is discontinued from the study before completing Visit 6/Exit (Month 5) (D141±7)), then to the extent possible, all assessments, including safety, that are scheduled to be performed at Visit 6/Exit should be performed on the day of discontinuation.

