2 SYNOPSIS

Name of Sponsor/Company: RIBOMIC USA Inc. [name]	
Name of Investigational Product: RBM-007 injectable solution	
Name of Active Ingredient: RBM-007	
Title of Study: A Multi-Center, Open Label, TOFU Extension Study Assessing the Efficacy and Safety of Additional Intravitreal Injections of RBM-007 in Subjects with Wet Age-related Macular Degeneration – RAMEN Study	
Study Period: Approximately 12 months Estimated date first subject enrolled: October 2020 Estimated date last subject completed: November 2021	Phase of Development: Phase II
Primary Objective: To assess the safety and efficacy of additional intravitreal injections of RBM-007 (2.0 mg/eye) in subjects with wet age-related macular degeneration (AMD) rolled over from TOFU Study (Protocol RBM-007-002).	
Secondary Objective: To evaluate anti-fibrotic effect for RBM-007 in subjects with exudative age-related macular degeneration.	

Methodology:

This is a multi-center, open label, extension study assessing the efficacy and safety of additional intravitreal injections of RBM-007 in subjects with wet age-related macular degeneration.

Subjects who meet all eligibility criteria at the time of exit visit of TOFU study will receive treatment for up to three months in the study eye. Subjects that successfully exited TOFU study on or before approximately September 1, 2021 will be considered for RAMEN Study.

Approximately forty subjects with exudative age-related macular degeneration (AMD) will receive RBM-007 injectable solution (2.0 mg/eye)

The primary endpoint of the study is at one month post the last injection with safety evaluation through two months post the last injection.

For eligibility, subjects must be diagnosed with exudative AMD in the study eye, for which previous TOFU masked treatment arms with intravitreal anti-vascular endothelial growth factor (anti-VEGF) agent Eylea® and/or RBM-007 has not demonstrated improvement in vision, with less than 15 letter BCVA improvement in TOFU study at the exit visit of TOFU over its baseline. Subjects must have completed all visits in the TOFU study.

Subject must demonstrate absence of central atrophy or retinal epithelial tear in the fovea or any condition preventing VA improvement in the study eye.

Eligible subjects who are enrolled in the study will be seen for at least 6 visits that include a Baseline/Day 1 (Visit 1), and months 1-5 (Visit 2-6)

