7 INVESTIGATIONAL PLAN

7.1 Overall Study Design and Plan

This is a multi-center, open label, extension study assessing the efficacy and safety of additional intravitreal injections of RBM-007 in subjects with wet age-related macular degeneration rolled over from TOFU Study.

Subjects who meet all eligibility criteria at the time of exit visit of TOFU study will receive treatment for up to three months in the study eye. Subjects that successfully exited TOFU study on or before approximately September 1, 2021 will be considered for RAMEN Study.

Approximately forty subjects with exudative age-related macular degeneration (AMD) will receive RBM-007 Injectable Solution (2.0 mg/eye).

The primary endpoint of the study is at one month post the last injection with safety evaluation through additional two months post the last injection.

For eligibility, subjects must be diagnosed with exudative AMD in the study eye, for which previous TOFU masked treatment arms with intravitreal anti-vascular endothelial growth factor (anti-VEGF) agent Eylea® and/or RBM-007 has not demonstrated improvement in vision, with less than 15 letter BCVA improvement in TOFU study at the exit visit of TOFU over its baseline. Subjects must have completed all visits in the TOFU study.

Subject must demonstrate absence of central atrophy or retinal epithelial tear in the fovea or any condition preventing VA improvement in the study eye.

Eligible subjects who are enrolled in the study are expected to be seen for at least 6 visits that include a Baseline/Day 1 (Visit 1), and months 1-5 (Visit 2-6).

Subjects are eligible for rescue with Eylea® or other treatment at the discretion of investigator anytime during the study if one of the following rescue criteria is met.

Rescue Criteria:

Eligibility criteria for Rescue are as follow:

- BCVA decrease of > 10 letters AND central subfield thickness (CST) increase of > 50 μ m from RAMEN baseline visit.
- The discretion of investigator.

Rescue therapy is defined as IVT injection of Eylea® or other treatment at the discretion of investigator in the study eye.

Whenever possible, RIBOMIC should be notified before any rescue procedure.

If rescue with anti-VEGF agent is considered, the subject must receive the injection of RBM-007 scheduled for the specific visit prior to the injection of anti-VEGF agent for rescue.

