12.1.1.2 Reporting Adverse Events

AEs, whether spontaneously reported by the subject or noted by authorized study personnel, will be recorded in the subject's medical record and on the appropriate AE eCRF. Each recorded AE will be described by its duration (i.e., start and end dates), frequency, severity, regulatory seriousness criteria if applicable, suspected relationship to the study drug(s), relation to injection procedure, location, actions taken and outcome.

AEs that occur after any subject has provided written informed consent, before treatment, during treatment, or within 30 days following the cessation of treatment, whether or not they are related to the study, must be recorded. To improve the quality and precision of acquired AE data, Clinical Investigators should observe the following guidelines:

- Whenever possible, use recognized medical terms when recording. Do not use colloquialisms and/or abbreviations.
- If known, record the diagnosis (i.e., disease or syndrome) rather than component signs and symptoms and /or laboratory or test findings (e.g., record congestive heart failure rather than dyspnea, rales, and cyanosis, and enlarged heart on chest x-ray). However, other events that are considered unrelated to an encountered syndrome or disease should be recorded as individual AEs (e.g., if congestive heart failure and severe headache are observed at the same time and are clinically unrelated, each event should be recorded as an individual AE).
- If the diagnosis is not known, then record the leading component sign, symptom or test finding and describe the other clinically related findings in the narrative description of the case. A suspected diagnosis can be used and described as such.

- (e.g., record suspected or probable myocardial infarction); this has to be updated in the clinical database once the diagnosis is confirmed.

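### Section 8.3 provides only for leaving the study, with the last examination that same day; new AEs in leavers then have a recording window but no scheduled contact, and obtainable Month 4 BCVA is imputed

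*Protocol*

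**What the plan says.** Section 8.3 defines early termination as the case where a consented subject "ceases participation in the study, regardless of circumstances, before the completion of the study". Its listed reasons include AEs, non-compliance and protocol violation, as well as death, loss to follow-up and withdrawal by the subject. The investigator or the Medical Monitor may also end participation in the subject's interest. The rule that follows begins "If a subject is discontinued from the study before completing Visit 6/Exit" and provides that, to the extent possible, "all assessments, including safety, that are scheduled to be performed at Visit 6/Exit should be performed on the day of discontinuation". No later visit or contact is named, and the section does not mention a subject who stops injections but remains in the study.

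Five other places bear on follow-up:

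- The synopsis describes "safety evaluation through two months post the last injection". Section 7.1 has "safety evaluation through additional two months post the last injection".
- Section 12.1.1.2 covers AEs that occur "within 30 days following the cessation of treatment, whether or not they are related to the study, must be recorded".
- Section 12.2.12 has AEs elicited from screening up to study exit.
- Section 12.1.4 has AEs reported at exit followed until they resolve or reach a settled state, and lets the sponsor ask for follow-up beyond the end of the study.
- Section 14.4 imputes missing post-injection efficacy values by LOCF.

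**The concern.** Safety is part of the primary objective, and Section 12.1.1 itself warns of endophthalmitis and retinal detachment after intravitreal injection. Subjects who leave early have the shortest scheduled observation after their last injection, and some of them leave because something went wrong. If new events after exit are not looked for, the safety summary leans towards those who tolerated all four injections.

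The primary efficacy variable is exposed as well. A subject removed by the investigator or Medical Monitor may be perfectly willing to return. Under Section 8.3 that subject's Month 4 BCVA is not collected, and an earlier value stands in for it.

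**Working it through.** **Inputs.** Injections are on Day 1, Day 29 ±4, Day 57 ±4 and Day 85 ±4; Visit 5 (Month 4, primary endpoint) is on Day 113 ±7; Visit 6/Exit is on Day 141 ±7 (Table 2 and Section 7.5.1). The AE window is 30 days after treatment ceases (Section 12.1.1.2); I take that to run from the last injection received, since the protocol does not define it further.

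**Step 1: the plan's own figure.** For a completer, Visit 6 minus last injection = 141 − 85 = 56 days, or two 28-day study months. With windows, the shortest is 134 − 89 = 45 days and the longest 148 − 81 = 67 days. The stated two months is reproduced.

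**Step 2: early leavers under Section 8.3.** Time from last injection to last scheduled examination:

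| Subject leaves | Nominal days | With windows | Short of 56 (nominal) |
|---|---|---|---|
| On an injection day, after the injection | 0 | – | 56 |
| At Visit 2, before injection | 29 − 1 = 28 | 24 to 32 | 28 |
| At Visit 3, before injection | 57 − 29 = 28 | 20 to 36 | 28 |
| At Visit 4, before injection | 85 − 57 = 28 | 20 to 36 | 28 |
| At Visit 5 | 113 − 85 = 28 | 17 to 39 | 28 |

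A subject who leaves between Visits 5 and 6 has more than 28 nominal days and already has a Month 4 BCVA.

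**Step 3: the 30-day AE window.** Completers always clear it, because their shortest windowed follow-up (45 days) exceeds 30. The conflict between Sections 12.1.1.2 and 12.2.12 therefore arises only for early leavers. A subject who exits on an injection day has 30 days in which recording is mandatory but no contact is scheduled. One who exits at the next nominal visit has 30 − 28 = 2 such days. Even if fully observed, the window covers 30/56 = 54% of the two-month period. For a leaver, days 31 to 56 have no rule for collecting new AEs.

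**Step 4: the primary endpoint.** Assume that the BCVA taken on the day of leaving is the value carried forward. A subject leaving at Visit 2, 3 or 4 then has that value carried 113 − 29 = 84, 113 − 57 = 56 or 113 − 85 = 28 days to Month 4.

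**Step 5: weight.** With about 40 subjects, each leaver is 1/40 = 2.5% of the planned sample. No drop-out rate is given, so the total cannot be computed.

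**The case against.** Several stronger readings are tempting, and the protocol does not support them.

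- **A reader might infer that safety follow-up stops altogether on the day of discontinuation, above all for AE leavers.** It does not. Section 12.1.4 follows AEs open at exit, and Section 12.1.1.1 has investigators ask about AEs at every subject contact, so those contacts may also bring new events to light. Subjects who leave because of an AE are the best covered in this respect. What stands is that such contacts are not scheduled, need not include BCVA, IOP, ophthalmoscopy or OCT, and do not exist for a leaver with no open AE.
- **A reader might infer that the protocol forbids stopping injections while staying in the study.** That would be an inference from silence. Sections 7.1 and 7.1.1 give treatment duration and total amount as maxima, Section 7.4 foresees the Safety Review Team stopping doses, and the termination wording in Section 8.3 is permissive. Section 12.1.3 even keeps a pregnant subject under follow-up after removal. The route is not barred, but it is not written down, and Section 8.3 as it stands directs staff to an exit visit.
- **A reader might take the two-month sentences as a guarantee to every subject.** They describe the planned schedule, which Visit 6 delivers for completers.

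Two further points against the concern are fair. Death, loss to follow-up and full withdrawal of consent cannot be remedied by any wording. And the study is exploratory and descriptive with no hypothesis (Section 14.2.2), so no formal test is at risk. Neither point disposes of subjects removed by decision of the investigator or Medical Monitor who would still attend, nor of the mismatch between Sections 12.1.1.2 and 12.2.12.

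**Conclusion.** The concern holds in limited form. For subjects who leave by the next planned visit, the last scheduled examination falls 0 to about 28 days after the last injection, against 56 (45 to 67) for completers. New AEs in leavers have a mandatory 30-day recording window with between 2 days (exit at the next nominal visit) and 30 days (exit on an injection day) not served by any scheduled contact, and no collection rule at all from day 31 to day 56. Month 4 BCVA that could have been observed is imputed instead.

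This rests on nominal visit days, on counting the window from the last injection, and on the exit BCVA being the value carried forward. It concerns only leavers who could still be seen or reached. How many that is cannot be said from the protocol. In a study of about 40 whose primary objective includes safety, it is worth correcting.

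**What to change.** 1. In Section 8.3, state that a subject who no longer receives RBM-007 but still consents remains in the study for the assessments already scheduled, including the Month 4 BCVA.
2. For a subject who leaves the study, keep the day-of-discontinuation assessments and, where consent allows, add one AE contact timed to close the post-treatment AE window. A telephone call is enough.
3. Reconcile the synopsis and Sections 7.1, 8.3, 12.1.1.2, 12.1.4 and 12.2.12 so that a single AE follow-up period applies. The sponsor decides which period. In the same edit, align the two wordings of the two-month sentence, since the extra word in Section 7.1 could be read as a longer period.

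When injections are stopped is left as the protocol has it.

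The cost is a short amendment, visits that already exist, and one call per leaver. The downside is slight extra site time for the few concerned. A subject who stops after the Day 1 injection would be seen for up to 141 − 1 = 140 days, longer than a completer's 56 days after the last injection; that extra time is the price of an observed Month 4 BCVA.
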